Our community, known as the CHARM Consortium (cfDNA in Hereditary And High-Risk Malignancies), was founded in 2018 to address HCS knowledge and delivery gaps through evaluation of blood-based cfDNA testing. Comprised of 8 genetics clinics from 5 Canadian provinces, CHARM is a patient-engaged biobanking and clinical data annotation service, where blood and available tumour samples are collected from HCS carriers at annual screening visits. Analysis of these samples has led to new advancements in cfDNA sequencing that we propose to test with this prospective trial, by evaluating the detection rate of cfDNA sequencing and the clinical benefit gained by following up on detection of early cancer using cfDNA. Specifically, we have demonstrated the use of three technologies to detect early cancer in HCS through analysis of cfDNA in blood plasma: 1) the CHARM gene panel, a targeted sequencing approach that provides in-depth mutational data on a core set of genes frequently mutated in FCS tumours and offered clinically by our program, 2) cell-free methylated DNA immunoprecipitation and high-throughput sequencing (cfMeDIP-seq), which can detect the specific organ from which the cancer-triggering DNA changes arise, and 3) shallow whole genome sequencing (sWGS), which detects accumulated mutations, copy number alterations and DNA fragmentation patterns that occur secondary to the inherited mutation. These results have suggested that integration of mutation, copy number, and functional (methylation or fragmentation) aspects of cfDNA provide the greatest sensitivity for early HCS detection.

In this study, we will enroll 1,000 patients from across Canada's HCS screening programs. Half of the patients will be randomized to have cfDNA analysis with results returned to managing physicians who will follow-up any abnormal cfDNA findings with appropriate clinical imaging and heightened surveillance. At the end of this study, the rate of cancer detection using cfDNA-informed surveillance will be compared with the rate of detection in the cohort of patients who did not receive the result of the cfDNA test but were managed according to current conventional screening programs.

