4.1 Overall Study Design

We are conducting a randomized control trial to assess the use of cfDNA analysis in cancer surveillance protocols for patients with HCS. We will recruit 1,000 patients across Canada with a known/suspected genetic diagnosis of one of the following HCS: HBOC, LS, NF1, LFS, PALB2, or HDGC that are receiving standard-of-care clinical assessment for cancer by a managing physician under a provincial screening program or cancer surveillance protocol.

The study design is illustrated in Figure 1. At study enrollment, participants will be randomized to a control cohort (n=500) or an experimental cohort (n=500), stratifying for genetic HCS background. All participants in the experimental cohort will provide blood samples tri-annually (every four months) for four years, either at the study hospital, or at a local blood laboratory (e.g., LifeLabs or Dynacare). Whenever possible, patients will have research blood collected at the same time as routine blood collections for clinical purposes, to avoid additional venipunctures. Participants randomized to the control cohort will have the option to donate samples to the CHARM Consortium Biobank, for use in future research. Participants in the control cohort can donate between 1-3 blood samples a year, for the duration of the study.

Participants in both the control and experimental cohorts will continue to receive standard-of-care cancer surveillance according to current guidelines, as they were prior to study enrollment. Blood samples from the experimental cohort will be subject to a

Figure 1. Study Design.

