cfDNA sequencing assay, and results will be communicated to participants by the study team. Participants who receive a “positive” cfDNA assay result will be offered follow-up diagnostic procedures to confirm or rule out the presence of a malignancy. The diagnostic investigations are outlined in “Cohort Specific Diagnostic Workflows”, appended to this protocol. If an abnormality is identified by a diagnostic investigation done in follow-up to a “positive” cfDNA assay result, additional investigations (e.g., imaging or biopsy) will be performed as part of the participants clinical care, and will be guided by the participant’s clinical team, or study investigator. All participants will be followed by the study team for a minimum of 5 years, from their first blood collection. To assess the efficacy of the cfDNA assay, we will compare cfDNA assay results to the results of the participants standard of care cancer surveillance results.

Lastly, we will use questionnaires and semi-structured interviews to explore participants’ experiences with cfDNA testing, to understand perceptions of the clinical utility of cfDNA tests for HCS management and identify factors facilitating or impeding the uptake of this test in HCS management and patient decision making.

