7.0 Assessment of Efficacy and Safety

There is a possibility that the sequencing tests (sWGS, targeted panel, cfMeDIP) are less sensitive than standard-of-care screening. We will continuously monitor the concordance between cfDNA assay results and standard-of-care surveillance results. Confirmation of a cancer diagnosis will be supported by imaging confirmation, pathologic confirmation, or another form of clinical confirmation deemed appropriate by the study investigator. Yearly, we will evaluate:

- the percentage of cancers found by standard-of-care screening missed by the cfDNA assay.
- the percentage of positive cfDNA results where no cancer is detected on any follow-up diagnostic investigations.

If we determine that one of the tests are consistently underperforming (e.g. if 50% of cancers found by standard of care screening are missed by cfDNA assay), we will consider discontinuing the underperforming assay, and replacing it with an alternative validated test (e.g. plasma WGS). If we change one or more of the assays over the course of the study, participants will be notified of this change verbally by a study team member. If no alternative test is available, we may decide to end the study early.

The Study Doctor will perform the following tasks to ensure the safety of subjects and the good conduct of the study, on a monthly basis:

- Review the study binder to ensure all documents and communications are up to date
- Review the Inclusion/Exclusion forms for completeness and compliance to study protocol
- Monitor the accrual rate and recruiting efforts
- Monitor the number of ‘false positive’ results, and the number of subsequent diagnostic investigations undergone by the participant
- Monitor participant compliance to routine cancer screening protocols

Study related adverse events will be documented and reported to the UHN REB, as per the standard institutional procedure.

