8.0 Statistics

We will compare the cancer detection rate between control and experimental cohorts. Analysis will be stratified by the type of the tumours detected within each HCS, as well as across the entire cohort. Between the cohorts, we will first compare the cancers detected to ascertain whether cfDNA testing results in a more sensitive detection of clinically confirmed cancers, as well as calculate negative and positive predictive values of cfDNA findings as confirmed by clinical testing (MRI, ultrasound, biopsy, protein biomarkers, etc.). This analysis will also ascertain whether cfDNA is more or less effective at detecting specific cancer types compared to standard-of-care screening alone.

We will also conduct comparisons that compare categorical (e.g. cancer stage) and continuous time course data (e.g. time to symptom development, time to treatment, and time on treatment). The first comparison is a stage shift analysis, whereby we will assess whether cancers are being detected at earlier stages using cfDNA versus screening results from the same programs. Categorical variables of stages I-IV within each cancer type as defined by NCCN criteria will be compared using Pearson's χ^2 test. Binary comparison of “early” and “late” stage across all cancer types will be performed using Fisher Exact test. The second comparison will be calculation of the time to first treatment relative to the date of the last annual clinical screening visit. This comparison of continuous variables using the t-test will establish whether triannual cfDNA testing accelerates off-cycle clinical follow-up and medical treatment compared to waiting for annual clinic visits. The third comparison will compare mortality and morbidity specifically for pancreas, esophagus, brain, lung, and stomach cancers. We will calculate the time between detection of a cancer and when patient manifest symptoms of cancer (morbidity 1), how long patients are afflicted with cancer symptoms after detection and during treatment (morbidity 2), and how long a patient undergoes treatment before succumbing to disease (mortality) or, in the case of effective treatments, the time until treatment is discontinued, or patients transition to the outpatient setting. Continuous variables will be compared by t-test.

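### Section 8.0 words the stage-shift groups by how a cancer was found, not by randomised arm, and so permits a non-randomised comparison

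*Protocol*

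**What the plan says.** Section 8.0 (Statistics) introduces stage shift as the first of its further comparisons. The aim is to "assess whether cancers are being detected at earlier stages using cfDNA versus screening results from the same programs". Stages I to IV within each cancer type go to Pearson's chi-square test. The early/late comparison "stage across all cancer types will be performed using Fisher Exact test".

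Elsewhere the same section names the randomised groups. It opens with "We will compare the cancer detection rate between control and experimental cohorts" and goes on: "Between the cohorts, we will first compare the cancers detected to ascertain whether cfDNA testing results in a more sensitive detection of clinically confirmed cancers". Its last paragraph also compares rural and remote drop-out across arms.

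Two other places bear on which cancers will exist:
- Section 4.1: "Participants in both the control and experimental cohorts will continue to receive standard-of-care cancer surveillance according to current guidelines".
- Section 7.0 plans a yearly count of cancers that screening found and cfDNA missed, and gives as an example of an underperforming test "if 50% of cancers found by standard of care screening are missed by cfDNA assay".

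Section 2.1 also contrasts the cohorts: detection under cfDNA-informed surveillance "will be compared with the rate of detection in the cohort of patients who did not receive the result of the cfDNA test". That sentence concerns the detection rate, not stage. No section says that stage is compared by arm, and none says that cancers missed by cfDNA are excluded or moved.

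**The concern.** Whether a cancer is found by cfDNA or by screening is settled after randomisation and is itself a result of the intervention. A comparison grouped by route of detection therefore loses the protection of randomisation.

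The group left unassigned is experimental-arm cancers found by standard screening after a negative cfDNA result. Sections 4.1 and 7.0 together imply that it will occur. Under the literal wording these cancers either drop out of the cfDNA side or count as screening results. The result then depends on which stages shed detectable cfDNA, and not on whether offering the test shifts stage. A test that sees late disease better would look harmful between identical arms, and one that sees early disease better would look beneficial.

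Stage shift is the second of three aims in the Protocol Summary, and earlier-stage detection is part of the hypothesis in section 3.2, so the result will be read as a main finding.

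**Working it through.** The protocol states no figure for the stage analysis, so there is none to reproduce. The steps below show the mechanism on assumed inputs.

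**Inputs from the protocol.** 500 participants per arm (4.1); diagnosis rates of 5% without cfDNA and up to 10% with it (8.0); Fisher's exact test for early/late stage (8.0). Cancers per arm: 0.05 × 500 = 25 and 0.10 × 500 = 50.

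**Assumed inputs.** The share of cancers that are early, e, is equal in both arms, so there is no true shift. cfDNA sensitivity is dE for early and dL for late cancers. Cancers that cfDNA misses are found by other means.

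**Step 1: early share among cfDNA-found cancers.** The formula is e·dE / [e·dE + (1 − e)·dL]. Take 25 cancers per arm, 15 early and 10 late, so 15/25 = 60% early.

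| dE / dL | cfDNA-found: early, late | Early share, cfDNA-found | Control arm | Controls plus cfDNA-missed |
|---|---|---|---|---|
| 30% / 80% | 4.5, 8 | 4.5/12.5 = 36% | 60% | 25.5/37.5 = 68% |
| 40% / 70% | 6, 7 | 6/13 = 46% | 60% | 24/37 = 65% |
| 70% / 30% | 10.5, 3 | 10.5/13.5 = 78% | 60% | 19.5/36.5 = 53% |
| 50% / 50% | 7.5, 5 | 7.5/12.5 = 60% | 60% | 22.5/37.5 = 60% |

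The last column adds the missed cancers to the 15 early and 10 late controls; in row 1 the missed cancers are 10.5 early and 2 late. Counting every cancer by arm gives 60% against 60% in all rows.

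**Step 2: false-positive rate of the planned Fisher test.** Simulation with 4,000 replicates, e = 60% in both arms, 25 control cancers, and nominal two-sided 5%. The share of replicates rejected:

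| Experimental cancers | dE / dL | All cancers by arm | cfDNA-found v controls | cfDNA-found v all other cancers |
|---|---|---|---|---|
| 25 | 30% / 70% | 3.4% | 16.3% | 30.9% |
| 25 | 70% / 30% | 3.0% | 13.2% | 24.6% |
| 50 | 30% / 70% | 4.2% | 25.6% | 63.3% |
| 50 | 70% / 30% | 4.2% | 22.3% | 61.9% |
| 50 | 50% / 50% | 4.6% | 3.8% | 3.7% |

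With 35 experimental cancers (7% of 500) the results lie in between. The simulation standard error is at most √(0.5 × 0.5 / 4,000) = 0.8 points.

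**Step 3: is naming the arms enough?** Stage is known only for diagnosed cancers, and the design expects more diagnoses in the experimental arm. Suppose that arm has 50 cancers, 40 early and 10 late, against 15 early and 10 late in controls. The early share is 40/50 = 80% against 15/25 = 60%, yet late-stage cancers per randomised participant are 10/500 = 2.0% in both arms. The share has shifted with no fall in late disease. The count per randomised participant shows this; the share among cancers does not.

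**The case against.** The best reply is that the cfDNA side of the sentence is shorthand for the experimental cohort. Section 8.0 opens with a comparison of cohorts and adds stage shift as a further comparison. Section 2.1 describes controls as managed under conventional screening programmes, so the other side of the sentence can mean the control arm. This stands as a possible reading. A reader might infer from the sentence that the protocol has settled on a comparison by detection method and that randomisation is lost; the text does not go that far. It remains loose, because participants in both arms must be under a screening programme or surveillance protocol, so the phrase does not single out controls.

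A reader might also see the same fault in three other places:
- Section 4.1 says "we will compare cfDNA assay results to the results of the participants standard of care cancer surveillance results". That concerns the accuracy of the assay, where comparison by test is appropriate.
- Endpoint 2 in section 4.11 names controls as its comparator and is not ambiguous.
- Endpoint 3 is a detection rate with no comparator. Arm-against-arm wording would change it, not clarify it.

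Nor does any passage describe collecting data on programme patients outside the trial for comparison.

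It is also fair that stage shift is neither the primary objective nor one of the four listed endpoints, and that an SAP may define the analysis set. But the protocol itself states the contrast and its tests, so an SAP that followed the wording could carry out the non-randomised version. Lastly, the bias needs sensitivity that differs by stage; with equal sensitivity it disappears.

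**Conclusion.** The point holds as a defect of wording. Section 8.0 describes the stage-shift groups by detection method, and nothing elsewhere ties stage to the randomised arms. Taken literally, it allows cancers missed by cfDNA in the experimental arm to leave the cfDNA side or join the comparator. That produces a false stage difference in either direction whenever cfDNA sensitivity differs by stage.

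The size cannot be derived from the protocol, which gives no stage mix and no stage-specific sensitivity. On the assumed inputs above, Fisher's test rejects in about 13% to 26% of replicates (cfDNA-found against controls) or 25% to 63% (cfDNA-found against all other cancers), compared with about 3% to 4% by arm. These figures illustrate the mechanism and do not forecast this trial. The change should be made, since it costs little and protects one of the stated aims.

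**What to change.** In the stage-shift sentence of section 8.0, replace the description of the two groups with: *in participants randomised to the experimental arm versus participants randomised to the control arm, counting all cancers however found*. Tabulate mode of detection within the experimental arm as description only, without a test.

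Because stage among diagnosed cancers still conditions on diagnosis, add the number of late-stage cancers per randomised participant in each arm, using the same early/late definition as the Fisher comparison.

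Leave section 4.1 and endpoints 2 and 3 in section 4.11 as they are on this point. The cost is a wording change in the protocol, carried into the SAP if there is one. Section 4.8 already provides for pathology and imaging results on participants diagnosed during the study, so no new procedure is needed.

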LIBERATE – LIquid Biopsy Evaluation and Repository Development AT PrincEss Margaret
LFS – Li-Fraumeni Syndrome
Lynch/LS – Lynch Syndrome
MOHCCN - Marathon of Hope Cancer Centre Network
MTA - Material Transfer Agreement
MRN - Medical Record Number
NF1 – Neurofibromatosis Type 1
NPV - Negative Predictive Value
OICR - Ontario Institute for Cancer Research
PHI - Personal Health Information
PPV - Positive Predictive Value
SOP – Standard Operating Procedure
sWGS – Shallow Whole Genome Sequencing
TIDHI - Toronto Immune Digestive Health Institute
TP – Targeted Panel

Protocol Summary

CfDNA in Hereditary And High-risk Malignancies (CHARM) 2: Evaluating the Performance of a cfDNA Blood Test for Early Cancer Detection

Randomized Control Study

Sample Size

Total = 1000 patients with Hereditary Cancer Syndromes (HCS)

N = 500 (experimental arm)

N = 500 (control arm)

If other sites join our study, the appropriate MTAs and DTAs will be established, and samples collected at other institutions (who have institutional REB approval for the study) will be sent to UHN/OICR for analysis. Other sites may include: BC Cancer Agency, Mount Sinai Hospital, SickKids Hospital, Women's College Hospital, Sunnybrook Hospital, McGill Research Institute, Jewish General Hospital, IWK Health Centre, Eastern Health, Alberta University.

We will recruit up to 1000 patients at UHN.

Study Population

Our study focuses on patients with a known Hereditary Cancer Syndrome (HCS).

Accrual Period

January 2024 – December 2024

Study Design

Through the CHARM Consortium (www.charmconsortium.ca), we have shown that cell-free DNA (cfDNA) profiling can enable more frequent cancer surveillance from readily accessible blood collections and can detect cancer at the same time or earlier than clinical screening approaches. We are now conducting a prospective, multi-center, randomized control trial of cfDNA testing of 1,000 HCS carriers to 1) compare cancer detection rates with and without cfDNA testing, 2) assess cancer stage shift and clinical impact reducing mortality and morbidity cancers, and 3) assess impact of access to cfDNA results on patients' quality of life and psychological distress.

Study Duration

January 2024 – December 2031

Study Agent/ Intervention/ Procedure

cfDNA sequencing (on a blood sample), tri-annually for 4 years.

Primary Objective

Decrease the time to cancer detection and disease management in HCS carriers receiving cfDNA sequencing results compared to controls.

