2.0 Background Information

2.1 Background and Rationale

Early cancer detection is the surest path to survival, even cure. As cancer progresses, genetic changes continue to amass, thereby making late-stage cancers more aggressive, harder to eradicate, and more lethal. People who are affected by a hereditary cancer syndrome (HCS) have this lived experience, as they are born with a genetic change that puts them at high risk for developing multiple cancers throughout their lifetime. Over 200,000 Canadians harbor mutations in one of the >100 genes that cause an HCS, some facing a 100% lifetime risk of developing cancer^{1,2}. To find these cancers in time for effective treatment, all of these carriers undergo highly specific medical imaging and physical exams on a biannual or annual basis, often travelling 100s of kilometers at significant personal stress, expense, and time investment. Sadly, many of these patients receive late-stage cancer diagnoses, necessitating immediate and often radical surgeries, radiation treatments, or enrollment in experimental clinical trials.

People who carry an HCS genetic variant describe themselves as “ticking cancer time bombs” as they await the accumulation of mutations during their lifetime that trigger cancer development³. Depending on cancer type, individuals may be able to enroll in publicly-funded annual surveillance programs that are cancer-type specific and entail an array of comprehensive clinical exams and imaging modalities, such as full-body MRI, colonoscopies and mammograms. In HCS that predispose cancers for which early detection has not yet been possible, prophylactic surgeries are recommended, such as removal of breasts, ovaries, and fallopian tubes for carriers of Hereditary Breast and Ovarian Cancer (HBOC), removal of uterus and ovaries in Lynch Syndrome (LS), and gastrectomy for carriers of Hereditary Diffuse Gastric Cancer (HDGC)^{4,5,6}. These life-altering surgeries place a heavy psychological and physical burden on patients, particularly those of childbearing age who face uncertain timing of growing a family versus potential development of a cancer.

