3.0 Study Objectives and Hypothesis

3.1 Study Objectives

3.1.1 Primary Objective

Our primary study objective is to establish whether blood plasma cfDNA testing can detect cancers at the same time as, or earlier, than conventional standard-of-care screening tests for carriers of HCS. We will also assess the time to disease management in carriers receiving cfDNA sequencing results compared to controls.

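### Time to first treatment is counted from an undefined, post-randomisation screening visit: on one reading earlier treatment scores as later, on the other the gain is understated

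*Protocol*

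**What the plan says.** The Protocol Summary gives the primary objective as: "Decrease the time to cancer detection and disease management in HCS carriers receiving cfDNA sequencing results compared to controls". Section 3.1.1 repeats the second half: "We will also assess the time to disease management in carriers receiving cfDNA sequencing results compared to controls".

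Section 8.0 gives the analysis: "The second comparison will be calculation of the time to first treatment relative to the date of the last annual clinical screening visit". The arms are compared by t-test, and the purpose is to establish "whether triannual cfDNA testing accelerates off-cycle clinical follow-up and medical treatment compared to waiting for annual clinic visits". Section 8.0 contains no other between-arm analysis of time to first treatment, and no section defines which annual visit is the last one.

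Two design features matter here. Both arms keep their usual surveillance (Section 4.1), which Section 2.1 describes as "imaging and physical exams on a biannual or annual basis". In addition, "All participants in the experimental cohort will provide blood samples tri-annually (every four months) for four years".

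**The concern.** A between-arm time comparison needs an origin that means the same thing in both arms. This one does not. It falls after randomisation, and which visit it is depends on whether the cancer was found at a visit or between visits. Moving detection off-cycle is exactly what the intervention is meant to do, so the intervention shifts the origin as well as the outcome.

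Two visits fit the wording: the last one on or before detection, which may be the detecting visit, or the last clear one before detection. They give opposite signs. The trial is unblinded (Section 4.10), so the choice should not be left until data are in hand.

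The t-test also uses only participants who reach treatment. At the diagnosis rates in Section 8.0 (5%, rising to 10% with cfDNA), that is at most 0.05 × 500 = 25 controls and 0.10 × 500 = 50 experimental participants. This subgroup is formed after randomisation, and the intervention itself may change its size and make-up.

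**Working it through.** The protocol gives no figure for this comparison, so there is none to reproduce. The check has three parts.

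**Inputs from the protocol:** draws every 4 months (Section 4.1); report target 45 days (Section 4.5) and disclosure target 2 weeks (Section 4.6), so 59 days or about 1.9 months from draw to disclosure, taking receipt as the draw date; standard screening every 12 months (Section 2.1 also allows twice yearly).

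**Assumed, because the protocol gives none:** lag from detection to treatment L = 2 months; standard-screen sensitivity 60–95% (base 80%); cfDNA sensitivity per draw 30–70% (base 50%); mean time from detectability to symptoms 6–24 months (base 24).

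**1. Algebra.** Let r be the months from the last annual visit to an off-cycle detection.
- Reading A (the detecting visit counts): found at a visit, score = L; found off-cycle, score = r + L.
- Reading B (last clear visit): found at a visit, score = 12 + L; found off-cycle, score = r + L.

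If a share p of an arm's cancers is found off-cycle, the mean score is L + p·E(r) under A and 12 + L − p·(12 − E(r)) under B. Raising p, which cfDNA testing should do, raises A and lowers B. Neither score counts whole screening cycles saved, because the clock restarts at every visit that misses the cancer.

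**2. One cancer.** Draw at month 4, disclosed at 5.9, work-up assumed 1 month (6.9), treated at 8.9. The same cancer found at the month-12 visit is treated at 12 + 2 = 14. Treatment is 14 − 8.9 = 5.1 months earlier. Reading A scores 8.9 against 2.0, that is 6.9 months later. Reading B scores 8.9 against 14, the right direction.

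**3. Simulation** (400,000 cancers per setting, onset uniform between annual visits, no separate work-up time). Base case, months:

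| Measure | Control | cfDNA | Difference |
|---|---|---|---|
| True time to treatment | – | – | 2.4 earlier |
| Reading A | 4.06 | 6.45 | 2.4 later |
| Reading B | 12.66 | 11.20 | 1.5 earlier |

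The algebra accounts for these scores. B − A = 12(1 − p), so p = 1 − 8.60/12 = 0.28 in controls and 1 − 4.75/12 = 0.60 with cfDNA. E(r) = (4.06 − 2)/0.28, or about 7.3 months, and is nearly the same in the cfDNA arm. What separates the arms on either reading is almost entirely the off-cycle share.

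Sensitivity of the result:
- 24 months to symptoms, over the grid of sensitivities: Reading A is 1.6 to 3.1 months the wrong way, while true treatment is 0.9 to 5.0 months earlier.
- 6 months to symptoms, same grid: Reading A is about 0.4 to 1.0 months the wrong way.
- No standard screen for the cancer (annual visits still occur, 6 to 24 months to symptoms): every detection is off-cycle in both arms, so p = 1 and both readings score a difference of about 0. The true gain in the model is about 1.5 to 19 months.

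A differently built model (perfect annual screen, 1-month work-up, 0–50% of cancers found by symptoms between visits, cfDNA sensitivity 0.3–1.0) puts Reading A 0.95 to 4.9 months the wrong way. With one common origin for both arms, the cfDNA arm is 0.5 to 2.1 months earlier, which is the right sign.

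**The case against.** The strongest reply is that the authors meant the last clear visit. The purpose sentence speaks of treatment that "accelerates off-cycle clinical follow-up and medical treatment compared to waiting for annual clinic visits", which fits a clock running from the previous visit while a control patient waits for the next. On that reading the sign is right. This stands: a reader might infer that the plan will report benefit as harm, and the documents do not support that. The reversal needs the other reading, which the wording permits but does not state.

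A reader might also infer that the trial's main conclusion hangs on this test. It does not. Time to treatment is not among the four endpoints in Section 4.11, and Section 8.0 bases power on cancer detection. It is, however, half of the stated primary objective, and this t-test is the only between-arm analysis of time to first treatment in the protocol.

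The sizes rest on assumed inputs, and that stands too. With faster symptoms the reversal shrinks, and with no standard screen it vanishes, although the true gain then vanishes from the score as well.

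Twice-yearly programmes shorten the clock but give no reason to expect a bias between arms. Both arms keep their surveillance, and randomisation is by syndrome (Section 4.9).

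Finally, the precise date rule might be left to a SAP. But the protocol itself fixes the type of origin, the test and the inference, and choosing between the two visits does not repair them.

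**Conclusion.** The point holds as a badly chosen and undefined origin. Under either reading it is set after randomisation, depends on the mode of detection and restricts the comparison to treated patients.

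If the detecting visit counts, earlier treatment can score as later, illustratively by about 0.4 to 3 months for mean symptom times of 6 to 24 months. If the last clear visit is meant, which is the more natural inference from the purpose sentence, the direction is right but the gain is understated (1.5 against 2.4 months in the base case) and is about zero for cancers with no standard screening. Those cancers are a stated interest of the trial (Section 4.11, endpoint 3).

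The directions follow from the algebra, given that cfDNA testing raises the off-cycle share. The sizes depend on sensitivities, symptom times and treatment lags that the protocol does not give.

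**What to change.** In Section 8.0, replace this t-test with time from randomisation to first cancer treatment, compared by arm in all randomised participants: a time-to-event analysis, stratified by hereditary cancer syndrome, with untreated participants censored at the end of their follow-up.

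If the interval from a screening visit is still wanted, define it as starting at the last clear visit before detection and report it descriptively among treated patients, without a test. A lag from the first abnormal finding should not take its place as a between-arm comparison, because that origin is again set by the mode of detection. On the inputs above it would be about 1.9 + 2 = 3.9 months from a cfDNA draw against 2 months from a screen.

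The cost is a sentence or two in Section 8.0. Randomisation takes place at enrolment (Section 4.1), and treatment details and screening dates are already collected (Section 4.8); the date of first treatment should be confirmed as one of the treatment items. No study procedure or clinical care changes. The small downside is that the new estimate combines how many cancers are treated with how soon, and the protocol should say so.
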